9.4 Statistical Analyses

The statistical analysis plan will be finalised within 90 days of first subject in and it will include a more technical and detailed description of the statistical analyses described in this section. This section is a summary of the planned statistical analyses of the most important endpoints including primary and key secondary endpoints.

9.4.1 General Considerations

Statistical analyses will be performed by AstraZeneca or its representatives including CROs. No adjustments for multiplicity are planned.

9.4.2 Efficacy

9.4.2.1 Primary Endpoint(s)

9.4.2.1.1 Calculation or Derivation of Tumour Response Variables

9.4.2.1.1.1 Investigator RECIST 1.1-based assessments:

All RECIST 1.1 assessments, whether scheduled or unscheduled, will be included in the calculations. This is also regardless of whether a patient discontinues study treatment or receives another anti-cancer therapy.

At each visit, patients will be programmatically assigned a RECIST 1.1 visit response of CR, PR, stable disease, disease progression, or not evaluable depending on the status of their disease compared with baseline and previous assessments. Baseline will be assessed within the 21 days prior to randomisation (or first dose of study drug for the biopsy sub-study). The tumour response endpoints (ORR, DoR, BOR, TTR, PFS, and change in tumour size) will then be derived from the scan dates and overall visit responses.

9.4.2.1.1.2 BICR (Main study only):

A BICR of radiological scans will be performed on all patients in the main study to confirm the robustness of the investigator-assessed ORR, DoR, BOR, TTR, PFS, and change in tumour size endpoints.

All images will be collected centrally. The imaging scans will be reviewed by 2 independent radiologists using RECIST 1.1 and will be adjudicated, if required. For each patient, the BICR will define the overall visit response data (CR, PR, stable disease, disease progression, or not evaluable) and the relevant scan dates for each time point (ie, for visits where response or progression is/is not identified). Patients who have RECIST 1.1-defined disease progression on study treatment based on progression of non-target disease, may also require submission of additional scans/images/photographs eg, brain scan or photographs of cutaneous lesions. If a patient has had a tumour assessment that cannot be evaluated, then the patient will be assigned a visit response of not evaluable (unless there is evidence of progression, in which case the response will be assigned as disease progression). Endpoints ORR, DoR, BOR, TTR, and PFS will then be derived from the scan dates and overall visit responses.

The discordance between investigator assessment and BICR evaluation of measurable disease at baseline will be monitored. If the discordance is high (eg, > 5%), eligibility criteria may be amended to require measurable disease by BICR at baseline.

Further details of the BICR will be documented in an Independent Review Charter.

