- 9 BRAF V600E or V600K mutation status must be known at screening. Patients with BRAF mutant melanoma may have had a prior treatment regimen that included vemurafenib, dabrafenib, or an approved BRAF and approved MEK inhibitor. For country-specific requirements for France see Appendix K 1.2.
- 10 May have received a TKI (eg, imatinib) if c-kit mutant and available, or declined therapy.
- 11 Eastern Cooperative Oncology Group performance status 0 or 1, with no deterioration over the previous 2 weeks prior to baseline or day of first dosing.
- Measurable disease by RECIST 1.1. At least 1 lesion, not previously irradiated, that qualifies as a RECIST 1.1 target lesion (TL) at baseline and can be accurately measured at baseline as ≥ 10 mm in the longest diameter (except lymph nodes, which must have short axis ≥ 15 mm) with CT or MRI and is suitable for accurate repeated measurements. Tumour assessment by CT scan or MRI must be performed within 28 days prior to randomisation. Cutaneous lesions and other superficial lesions are not considered measurable disease lesions but may be considered as non-target lesions. For patients in the main study: if the patient has only 1 measurable lesion per RECIST 1.1, the biopsy specimen should be obtained from the non-target lesion or archival tissue.
- Patients with known CNS lesions should be asymptomatic, adequately treated with stereotactic radiation therapy, craniotomy, gamma knife therapy, or whole brain radiotherapy, with no subsequent evidence of CNS progression; patients must not require steroid exceeding > 10 mg prednisone or equivalent; patients with a history of central nervous system metastases must have MRI of the brain at screening. All AEs while receiving prior immunotherapy must have completely resolved, be medically controlled, or resolved to baseline prior to screening for this study.
- 14 Patients must have a life expectancy ≥ 3 months from proposed first dose date.

Weight

15 Body weight above 30 kg (> 30 kg).

Sex/Reproduction

- 16 Contraceptive use by men or women should be consistent with local regulations regarding the methods of contraception for those participating in clinical studies (Section 5.3.1).

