6.3.1.1 Screening Procedures

If a patient withdraws from the study, then his/her enrolment/randomisation code cannot be reused. Withdrawn patients will not be replaced.

Investigators should keep a record (ie, the patient screening log) of patients who entered screening.

At screening/baseline (Days -21 to -1), the investigators or suitably trained delegate will:

- Obtain signed informed consent before any study-specific procedures are performed. If laboratory or imaging procedures were performed for alternate reasons prior to signing consent, these can be used for screening purposes with consent of the patient. However, all screening imaging results must have been obtained within 28 days of randomisation and all screening laboratory results within 21 days of randomisation.
- Identify patients to the IWRS per country regulations. Obtain a unique 7-digit enrolment number (E-code), through the IWRS in the following format (ECCNNXXX: CC being the country code, NN being the centre number, and XXX being the patient enrolment code at the centre). This number is the patient's unique identifier and is used to identify the patient on the eCRFs.
- Determine patient eligibility (see Sections 5.1 and 5.2).
- Obtain signed informed consent for genetic research study (optional). Patients who decide not to sign the specific genetic ICF but the general study ICF are eligible for study enrolment and all other study procedures.

If the patient is ineligible and not randomised, the IWRS should be accessed to terminate the patient in the system.

Patients will begin treatment on Day 1. Treatment should start no more than 3 working days after being randomised. Patients must not be randomised and treated unless all eligibility criteria have been met.

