8.1 Efficacy Assessments

8.1.1 Tumour Assessments

Tumour response will be evaluated by the investigator and by BICR (main study only) according to RECIST 1.1. All treatment decisions will be based on on-site assessment of scans. Patients who are determined to have progressed according to RECIST 1.1 criteria by the investigator will have scans centrally reviewed for confirmation of objective disease progression. If disease progression is not confirmed at central review an additional RECIST 1.1 assessment may be requested preferably at the next scheduled RECIST 1.1 visit.

Baseline tumour assessments should encompass all areas of known predilection for metastases in the disease under evaluation and should additionally investigate areas that may be involved based on signs and symptoms of individual patients. Baseline assessments should be performed no more than 21 days before randomisation, and ideally should be performed as close as possible to the start of study treatment. The methods of assessment used at baseline should be used at each subsequent follow-up assessment.

Tumour assessment will be conducted every 8 weeks (± 1 week) after the start of treatment (Cycle 1 Day 1) up to 18 months, then every 12 weeks (± 1 week) until objective disease progression as per RECIST 1.1, irrespective of treatment decisions. In the event of treatment interruptions or delays, tumour assessments should proceed to schedule relative to Cycle 1 Day 1. Tumour assessments (RECIST 1.1) are to continue according to schedule in patients who discontinue treatment for reasons other than disease progression.

Any other sites at which new disease is suspected should also be appropriately imaged. If an unscheduled assessment is performed (eg, to investigate clinical signs and symptoms of progression) and the patient has not progressed, every attempt should be made to perform subsequent assessments at the scheduled visits whilst the patient remains on study treatment.

Digital colour photographs documenting measurable lesions including a ruler to estimate the size of the lesion, should be obtained if the cutaneous lesion is included as part of the non-target lesions for disease assessment according to RECIST 1.1. Copies of the photograph should be forwarded to the central imaging vendor for potential retrospective analysis. The timing for capturing cutaneous lesion photographs should follow the same schedule as the imaging scans.

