9.4.2.1.2 Objective Response Rate

Determination of ORR by BICR is the primary objective, and as a sensitivity analysis, ORR by investigator recorded assessments will also be evaluated. Objective response rate is defined

as the proportion of patients who have a CR or PR prior to any evidence of progression (as defined by RECIST 1.1) that is confirmed at least 4 weeks later. The primary analysis of objective response rate will be based upon the safety analysis set. A sensitivity analysis will also be provided in the subset of patients in the safety analysis set who also have measurable disease at baseline by BICR. Data obtained from randomisation up until progression, or the last evaluable assessment in the absence of progression, will be included in the assessment of ORR, regardless of whether the patient withdraws from therapy. Patients who discontinue treatment without a response or progression, receive a subsequent therapy, and then respond will not be included as responders in the ORR.

As primary analysis, ORR will be summarised for each treatment arm non-comparatively with 95% CI (Clopper-Pearson).

As a secondary objective, ORR will be compared between the treatment arms using logistic regression adjusting for PD-(L)1 resistance type and LDH per randomisation stratification as covariates. The results of the analysis will be presented in terms of an odds ratio for study treatments together with associated 95% profile likelihood CI and p-value (based on twice the change in in log-likelihood resulting from the addition of a treatment factor to the model). This comparative analysis will be provided using the full analysis set.

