9.4.2.2.3 Progression Free Survival

Progression free survival is defined as the time from the date of randomisation (or date of first dose for the biopsy sub-study) until the date of objective disease progression per RECIST 1.1 as assessed by BICR or death (by any cause in the absence of progression), (ie, date of event or censoring – date of randomisation/the first dose of study treatment + 1). PFS will be analysed using the full analysis set (main study) and the safety analysis set (biopsy sub-study), and will include all patients in the analysis set regardless of whether the patient withdraws from therapy or receives another anti-cancer therapy or clinically progresses prior to RECIST 1.1 progression. Patients who have not progressed or died at the time of analysis will be censored at the time of the latest date of assessment from their last evaluable RECIST assessment. However, if the patient progresses or dies immediately after 2 or more consecutive missed visits, the patient will be censored at the time of the latest evaluable RECIST assessment prior to the 2 missed visits (Note: Not evaluable visit is not considered as missed visit). If the patient has no evaluable visits or does not have baseline data, they will be censored at Day 1 unless they die within 2 visits of baseline (16 weeks plus 1 week allowing for a late assessment within the visit window).

The PFS time will always be derived based on scan/assessment dates and not visit dates.

RECIST 1.1 assessments/scans contributing toward a particular visit may be performed on different dates. The following rules will be applied:

- For investigator assessments, the date of progression will be determined based on the earliest RECIST assessment/scan dates of the component that indicates progression.
- For BICR assessments, the date of progression will be determined based on the earliest dates of the component that triggered the progression on the first set of scans that indicates progression for the adjudicated reviewer selecting disease progression per RECIST 1.1, or of either reviewer where both reviewers select disease progression per RECIST 1.1 as a time point response, and there is no adjudication for central review (BICR) data.
- When censoring a patient for PFS, the patient will be censored at the latest scan dates contributing to a particular overall visit assessment.

Analysis methods:

PFS will be analysed for both BICR and investigator recorded assessment.

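### The protocol gives two baseline imaging windows, 28 days and 21 days before randomisation; read literally, the 21-day analysis wording could leave some eligible patients without a baseline

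*Protocol*

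**What the plan says.** Two places in the protocol allow 28 days. Inclusion criterion 12 (Section 5.1.1) states "Tumour assessment by CT scan or MRI must be performed within 28 days prior to randomisation". Section 6.3.1.1 repeats the limit and sets it apart from the laboratory limit: "all screening imaging results must have been obtained within 28 days of randomisation and all screening laboratory results within 21 days of randomisation". The same section lets imaging done for other reasons before consent serve for screening.

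Two places allow 21 days. Section 8.1.1 states "Baseline assessments should be performed no more than 21 days before randomisation". Section 9.4.2.1.1.1, on investigator RECIST assessments, states "Baseline will be assessed within the 21 days prior to randomisation (or first dose of study drug for the biopsy sub-study"). The screening period itself runs from Day -21 to Day -1 (Section 6.3.1.1 and the schedules of activities).

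Two further passages set the consequence. On PFS, Section 9.4.2.2.3 says "If the patient has no evaluable visits or does not have baseline data, they will be censored at Day 1", with an exception for death within two visits of baseline (16 weeks plus 1 week). On the primary endpoint, Section 9.4.2.1.2 says "Determination of ORR by BICR is the primary objective, and as a sensitivity analysis, ORR by investigator recorded assessments will also be evaluated", and the analysis uses the safety analysis set.

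**The concern.** In the main study all four statements concern the same baseline scan and count back from randomisation. A patient scanned on day 25 before randomisation satisfies criterion 12 but falls outside the window in the section that derives response. That section assigns each visit response by comparison with baseline and then derives ORR, DoR, BOR, TTR, PFS and change in tumour size. If the 21-day sentence is programmed as a filter, this patient has no baseline. No response can then be derived, and the patient counts as a non-responder because the ORR denominator is all dosed patients. For PFS, the missing-baseline rule replaces an observed progression time with censoring at Day 1.

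The biopsy sub-study has a further mismatch. Criterion 12 applies to those patients too, but it counts from a randomisation that they do not undergo. Section 9.4.2.1.1.1 counts from their first dose.

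**Working it through.** **Step 1. Compare the windows.**

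| Place | Purpose | Window |
|---|---|---|
| 5.1.1, criterion 12 | Eligibility, measurable disease | 28 days |
| 6.3.1.1 | Screening imaging | 28 days (laboratory results: 21) |
| 8.1.1 | Conduct of tumour assessments | 21 days |
| 9.4.2.1.1.1 | Investigator response derivation | 21 days (from first dose in the sub-study) |
| 9.4.2.1.1.2 | Central review (BICR) | none stated |

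The gap is 28 - 21 = 7 days, and 7/28 = 25% of the window that eligibility allows. Section 6.3.1.1 gives imaging and laboratory results different limits in one sentence, so the 28 days is unlikely to be a slip. The conflict is not simply eligibility against analysis, because the conduct text in Section 8.1.1 also says 21 days.

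**Step 2. Trace which analyses the 21-day text governs.**

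- Investigator-assessed ORR, DoR, TTR, PFS and tumour size are sensitivity analyses in the main study (Table 5). They fall directly under Section 9.4.2.1.1.1.
- The biopsy sub-study's response and progression endpoints use investigator assessment (Table 6), so they also fall directly under it.
- Primary ORR and the main PFS, DoR, TTR and tumour-size analyses use BICR. Section 9.4.2.1.1.2 gives no window. Section 8.1.1.2 says the central review itself sets the overall visit response, without programmatic derivation. The only 21-day text that covers both assessors is Section 8.1.1.

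**Step 3. Illustrate the size.** The plan has no figure to reproduce here, and the design response rates are redacted. The share f of patients scanned on days 22 to 28 is not given, so 5% to 25% is assumed. The 25% end corresponds to scan dates spread evenly over 28 days. Assume also that every such scan is rejected and the patient counted as a non-responder. Then

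expected ORR = true ORR x (1 - f).

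The 30% rate is from the earlier combination study cited in Section 4.2; the 20% rate is an assumption.

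| f | Patients of 150 | True ORR 30% | True ORR 20% |
|---|---|---|---|
| 5% | 7.5 | 0.30 x 0.95 = 28.5% | 19.0% |
| 10% | 15 | 0.30 x 0.90 = 27.0% | 18.0% |
| 25% | 37.5 | 0.30 x 0.75 = 22.5% | 15.0% |

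With 100 patients in the combination arm, the exact 95% interval is 21.2% to 40.0% for 30 responders and 18.6% to 36.8% for 27 responders (f = 10%).

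For PFS, the same share f of patients would be at risk of censoring at Day 1, apart from those who die within 17 weeks. With a single common window f = 0 and there is no loss.

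**The case against.** The strongest reply is that no sentence rejects a scan from days 22 to 28. Section 9.4.2.1.1.1 says when baseline is to be assessed and gives no rule for scans outside that time. It also opens by including all RECIST assessments, scheduled or not. A patient with an evaluable scan on day 25 before randomisation has baseline data, so the Day 1 censoring rule need not apply. Handling of out-of-window scans may be settled in the SAP or the BICR charter, neither of which is at hand. This stands as far as the consequence goes: the loss depends on how the sentence is applied. It does not remove the contradiction, which lies in what the protocol states and not in a detail left for later.

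A reader might go further and infer that eligible patients scanned on days 22 to 28 definitely have no valid baseline, and that the primary ORR is therefore understated. The documents do not support that. The 21-day derivation sentence belongs to the investigator assessments, the BICR subsection has no window, and the 21 days in Section 8.1.1 is a conduct instruction, not an analysis exclusion.

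The assumed shares can also be challenged. Screening runs from Day -21, and Section 8.1.1 asks for scans close to the start of treatment. Older scans would mainly be those taken before consent, so 25% is probably high. Nor can the share of patients be read as the share of PFS follow-up lost.

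**Conclusion.** The protocol states two incompatible baseline imaging windows, with two passages on each side, and they need to be reconciled. The size of the effect is unknown because the number of patients scanned on days 22 to 28 is not given.

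The risk is conditional on literal use of the 21-day window. In that case it falls directly on the investigator-assessed sensitivity analyses and the sub-study's response and progression endpoints. It reaches the BICR-based primary ORR and PFS only if the Section 8.1.1 window is carried over. If only the investigator derivation used the shorter window, the two assessors could also disagree for reasons unrelated to how the scans were read. The response rates tabulated above show scale under stated assumptions and are not estimates for this trial.

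**What to change.** In Section 9.4.2.1.1.1, define baseline as the last evaluable tumour assessment within 28 days before randomisation, or before first dose in the biopsy sub-study. State that the definition applies to both the investigator and the BICR derivations. Align Section 8.1.1 with it, and list the patients whose baseline scan fell on days 22 to 28 so that the actual number is known.

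Aligning to 28 days is the practical direction. The summary of changes says the study is no longer recruiting, so a tighter window cannot alter scans already taken under criterion 12. The longer window keeps the baseline of every patient enrolled within it. The cost is a wording change in two sections and one listing, with no new data.

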9.4.2.1.2 Objective Response Rate

Determination of ORR by BICR is the primary objective, and as a sensitivity analysis, ORR by investigator recorded assessments will also be evaluated. Objective response rate is defined

as the proportion of patients who have a CR or PR prior to any evidence of progression (as defined by RECIST 1.1) that is confirmed at least 4 weeks later. The primary analysis of objective response rate will be based upon the safety analysis set. A sensitivity analysis will also be provided in the subset of patients in the safety analysis set who also have measurable disease at baseline by BICR. Data obtained from randomisation up until progression, or the last evaluable assessment in the absence of progression, will be included in the assessment of ORR, regardless of whether the patient withdraws from therapy. Patients who discontinue treatment without a response or progression, receive a subsequent therapy, and then respond will not be included as responders in the ORR.

As primary analysis, ORR will be summarised for each treatment arm non-comparatively with 95% CI (Clopper-Pearson).

As a secondary objective, ORR will be compared between the treatment arms using logistic regression adjusting for PD-(L)1 resistance type and LDH per randomisation stratification as covariates. The results of the analysis will be presented in terms of an odds ratio for study treatments together with associated 95% profile likelihood CI and p-value (based on twice the change in in log-likelihood resulting from the addition of a treatment factor to the model). This comparative analysis will be provided using the full analysis set.

9.4.2.2 Secondary Endpoints

9.4.2.2.1 **Duration of Response**

Duration of response will be defined as the time from the date of first documented confirmed response until date of documented progression per RECIST 1.1 as assessed by BICR or death due to any cause. Sensitivity analyses will report DoR using investigator-based assessments with programmatic derivation of the visit response. The end of response should coincide with the date of progression or death from any cause used for the PFS endpoint. The time of the initial response will be defined as the latest of the dates contributing towards the first visit response of PR or CR.

If a patient does not progress following a response, then their duration of response will use the PFS censoring time.

Descriptive data will be provided for the duration of response in responding patients, by Kaplan-Meier method including the medians, and landmark estimates at 6, 9, 12, 15, and 18 months with corresponding 95% CI.

